### 5.2.2 Timing of Dose Administration

Trial treatment should be administered on Day 1 of each cycle after all procedures/assessments have been completed as detailed on the Trial Flow Chart (Section 6.0). Trial treatment may be administered up to 3 days before or after the scheduled Day 1 of each cycle due to administrative reasons.

All trial treatments will be administered on an outpatient basis.

Pembrolizumab 200 mg will be administered as a 30 minute IV infusion every 3 weeks. Sites should make every effort to target infusion timing to be as close to 30 minutes as possible. However, given the variability of infusion pumps from site to site, a window of -5 minutes and +10 minutes is permitted (i.e., infusion time is 30 minutes: -5 min/+10 min).

sEphB4-HSA will be administered as a 60 minute +/- 10 min infusion every week. The infusion will be initiated after completion of the pembrolizumab infusion.

The Each Pharmacy Manual contains specific instructions for the preparation of the pembrolizumab sEphB4-HSA and infusion fluid and administration of infusion solution.

### 5.2.3 Trial Blinding/Masking

This is a single arm, non-randomized, open-label trial; therefore, the Sponsor, investigator and subject will know the treatment administered.

### **5.3 Concomitant Medications/Vaccinations (allowed & prohibited)**

Medications or vaccinations specifically prohibited in the exclusion criteria are not allowed during the ongoing trial. If there is a clinical indication for one of these or other medications or vaccinations specifically prohibited during the trial, discontinuation from trial therapy or vaccination may be required. The investigator should discuss any questions regarding this with the Merck Clinical team. The final decision on any supportive therapy or vaccination rests with the investigator and/or the subject's primary physician.

#### **5.3.1 Acceptable Concomitant Medications**

All treatments that the investigator considers necessary for a subject's welfare may be administered at the discretion of the investigator in keeping with the community standards of medical care. All concomitant medication will be recorded on the case report form (CRF) including all prescription, over-the-counter (OTC), herbal supplements, and IV medications and fluids. If changes occur during the trial period, documentation of drug dosage, frequency, route, and date may also be included on the CRF.

All concomitant medications received within 28 days before the first dose of trial treatment and 30 days after the last dose of trial treatment should be recorded. Concomitant medications administered after 30 days after the last dose of trial treatment should be recorded for SAEs and ECIs as defined in Section 7.2.

#### **5.3.2 Prohibited Concomitant Medications**

Subjects are prohibited from receiving the following therapies during the Screening and Treatment Phase (including retreatment for post-complete response relapse) of this trial:

- Antineoplastic systemic chemotherapy or biological therapy
- Immunotherapy not specified in this protocol
- Chemotherapy not specified in this protocol
- Investigational agents other than pembrolizumab
- Radiation therapy
  - Note: Radiation therapy to a symptomatic solitary lesion or to the brain may be allowed at the investigator's discretion.
- Live vaccines within 30 days prior to the first dose of trial treatment and while participating in the trial. Examples of live vaccines include, but are not limited to, the following: measles, mumps, rubella, varicella/zoster, yellow fever, rabies, BCG, and typhoid vaccine.
- Systemic glucocorticoids for any purpose other than to modulate symptoms from an event of clinical interest or suspected immunologic etiology. The use of physiologic doses of corticosteroids may be approved after consultation with the Sponsor.

Subjects who, in the assessment by the investigator, require the use of any of the aforementioned treatments for clinical management should be removed from the trial. Subjects may receive other medications that the investigator deems to be medically necessary.

The Exclusion Criteria describes other medications which are prohibited in this trial.

There are no prohibited therapies during the Post-Treatment Follow-up Phase.

## 5.4 Rescue Medications & Supportive Care

### 5.4.1 Supportive Care Guidelines

Subjects should receive appropriate supportive care measures as deemed necessary by the treating investigator. Suggested supportive care measures for the management of adverse events with potential immunologic etiology are outlined below. Where appropriate, these guidelines include the use of oral or intravenous treatment with corticosteroids as well as additional anti-inflammatory agents if symptoms do not improve with administration of corticosteroids. Note that several courses of steroid tapering may be necessary as symptoms may worsen when the steroid dose is decreased. For each disorder, attempts should be made to rule out other causes such as metastatic disease or bacterial or viral infection, which might require additional supportive care. The treatment guidelines are intended to be applied when the investigator determines the events to be related to pembrolizumab.

Note: if after the evaluation the event is determined not to be related, the investigator does not need to follow the treatment guidance (as outlined below). Refer to Section 5.2.1 for dose modification.

It may be necessary to perform conditional procedures such as bronchoscopy, endoscopy, or skin photography as part of evaluation of the event.

- **Pneumonitis:**

- For **Grade 2 events**, treat with systemic corticosteroids. When symptoms improve to Grade 1 or less, steroid taper should be started and continued over no less than 4 weeks.
- For **Grade 3-4 events**, immediately treat with intravenous steroids. Administer additional anti-inflammatory measures, as needed.
- Add prophylactic antibiotics for opportunistic infections in the case of prolonged steroid administration.
- If there is recurrence of grade 2 pneumonitis, pembrolizumab will be permanently discontinued.

- **Diarrhea/Colitis:**

Subjects should be carefully monitored for signs and symptoms of enterocolitis (such as diarrhea, abdominal pain, blood or mucus in stool, with or without fever) and of bowel perforation (such as peritoneal signs and ileus).

- All subjects who experience diarrhea/colitis should be advised to drink liberal quantities of clear fluids. If sufficient oral fluid intake is not feasible, fluid and electrolytes should be substituted via IV infusion. For Grade 2 or higher diarrhea, consider GI consultation and endoscopy to confirm or rule out colitis.
- For **Grade 2 diarrhea/colitis**, administer oral corticosteroids.
- For **Grade 3 or 4 diarrhea/colitis**, treat with intravenous steroids followed by high dose oral steroids.
- When symptoms improve to Grade 1 or less, steroid taper should be started and continued over no less than 4 weeks.
- **Type 1 diabetes mellitus (if new onset, including diabetic ketoacidosis [DKA]) or ≥ Grade 3 Hyperglycemia, if associated with ketosis (ketonuria) or metabolic acidosis (DKA)**
  - For **T1DM or Grade 3-4 Hyperglycemia**
    - Insulin replacement therapy is recommended for Type I diabetes mellitus and for Grade 3-4 hyperglycemia associated with metabolic acidosis or ketonuria.
    - Evaluate patients with serum glucose and a metabolic panel, urine ketones, glycosylated hemoglobin, and C-peptide.
- **Hypophysitis:**
  - For **Grade 2** events, treat with corticosteroids. When symptoms improve to Grade 1 or less, steroid taper should be started and continued over no less than 4 weeks. Replacement of appropriate hormones may be required as the steroid dose is tapered.
  - For **Grade 3-4** events, treat with an initial dose of IV corticosteroids followed by oral corticosteroids. When symptoms improve to Grade 1 or less, steroid taper should be started and continued over no less than 4 weeks. Replacement of appropriate hormones may be required as the steroid dose is tapered.
- **Hyperthyroidism or Hypothyroidism:**

Thyroid disorders can occur at any time during treatment. Monitor patients for changes in thyroid function (at the start of treatment, periodically during treatment, and as indicated based on clinical evaluation) and for clinical signs and symptoms of thyroid disorders.

  - **Grade 2** hyperthyroidism events (and **Grade 2-4** hypothyroidism):
    - In hyperthyroidism, non-selective beta-blockers (e.g. propranolol) are suggested as initial therapy.
    - In hypothyroidism, thyroid hormone replacement therapy, with levothyroxine or liothyroinine, is indicated per standard of care.
  - **Grade 3-4** hyperthyroidism

- Treat with an initial dose of IV corticosteroid followed by oral corticosteroids. When symptoms improve to Grade 1 or less, steroid taper should be started and continued over no less than 4 weeks. Replacement of appropriate hormones may be required as the steroid dose is tapered.
- **Hepatic:**
  - For **Grade 2** events, monitor liver function tests more frequently until returned to baseline values (consider weekly).
    - Treat with IV or oral corticosteroids
  - For **Grade 3-4** events, treat with intravenous corticosteroids for 24 to 48 hours.
  - When symptoms improve to Grade 1 or less, a steroid taper should be started and continued over no less than 4 weeks.
- **Renal Failure or Nephritis:**
  - For **Grade 2** events, treat with corticosteroids.
  - For **Grade 3-4** events, treat with systemic corticosteroids.
  - When symptoms improve to Grade 1 or less, steroid taper should be started and continued over no less than 4 weeks.
- **Management of Infusion Reactions:** Signs and symptoms usually develop during or shortly after drug infusion and generally resolve completely within 24 hours of completion of infusion.

Table 2 below shows treatment guidelines for subjects who experience an infusion reaction associated with administration of pembrolizumab (MK-3475).

Table 3 Infusion Reaction Treatment Guidelines

NCI CTCAE Grade	Treatment	Premedication at subsequent dosing
Grade 1 Mild reaction; infusion interruption not indicated; intervention not indicated	Increase monitoring of vital signs as medically indicated until the subject is deemed medically stable in the opinion of the investigator.	None
Grade 2 Requires infusion interruption but responds promptly to symptomatic treatment (e.g., antihistamines, NSAIDS, narcotics, IV fluids); prophylactic medications indicated for <=24 hrs	
Stop Infusion and monitor symptoms. Additional appropriate medical therapy may include but is not limited to:
 
 
IV fluids
 
Antihistamines
 
NSAIDS
 
Acetaminophen
 
Narcotics
 
 
Increase monitoring of vital signs as medically indicated until the subject is deemed medically stable in the opinion of the investigator. If symptoms resolve within one hour of stopping drug infusion, the infusion may be restarted at 50% of the original infusion rate (e.g., from 100 mL/hr to 50 mL/hr). Otherwise dosing will be held until symptoms resolve and the subject should be premedicated for the next scheduled dose.
	
Subject may be premedicated 1.5h (<math>\pm</math> 30 minutes) prior to infusion of pembrolizumab (MK-3475) with:
 
Diphenhydramine 50 mg po (or equivalent dose of antihistamine).
 
Acetaminophen 500-1000 mg po (or equivalent dose of antipyretic).

NCI CTCAE Grade	Treatment	Premedication at subsequent dosing
	Subjects who develop Grade 2 toxicity despite adequate premedication should be permanently discontinued from further trial treatment administration.	
Grades 3 or 4  Grade 3: Prolonged (i.e., not rapidly responsive to symptomatic medication and/or brief interruption of infusion); recurrence of symptoms following initial improvement; hospitalization indicated for other clinical sequelae (e.g., renal impairment, pulmonary infiltrates)  Grade 4: Life-threatening; pressor or ventilatory support indicated	Stop Infusion. Additional appropriate medical therapy may include but is not limited to: IV fluids Antihistamines NSAIDS Acetaminophen Narcotics Oxygen Pressors Corticosteroids Epinephrine  Increase monitoring of vital signs as medically indicated until the subject is deemed medically stable in the opinion of the investigator. Hospitalization may be indicated. Subject is permanently discontinued from further trial treatment administration.	No subsequent dosing
Appropriate resuscitation equipment should be available in the room and a physician readily available during the period of drug administration.		

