## 5.2 Trial Treatments

The treatment to be used in this trial is outlined below in Table 2

Table 2 Trial Treatment

Drug	Dose/Potency	Dose Frequency	Route of Administration	Regimen/Treatment Period	Use
Pembrolizumab	200 mg IV	Q3W	IV infusion	Day 1 of each 3 week cycle	Experimental
sEphB4-HSA	10 mg/kg	Q1W	IV infusion	Day 1, 8,15 of each 3 week cycle	Experimental

Trial treatment should begin on the day of randomization or as close as possible to the date on which treatment is allocated/assigned. Trial therapy will continue up to 24 months, until disease progression, unacceptable toxicity, withdrawal of consent, investigator discretion, or sponsor decision to terminate the trial. Patients who stop therapy after 24 months and experience subsequent disease progression, may resume therapy for another 24 months.

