**Note: Permanently discontinue for any severe or Grade 3 drug-related AE that recurs or any life-threatening event.**

a For patients with liver metastasis who begin treatment with Grade 2 AST or ALT, if AST or ALT increases by greater than or equal to 50% relative to baseline and lasts for at least 1 week then patients should be discontinued.

b If symptoms resolve within one hour of stopping drug infusion, the infusion may be restarted at 50% of the original infusion rate (e.g., from 100 mL/hr to 50 mL/hr). Otherwise dosing will be held until symptoms resolve and the subject should be premedicated for the next scheduled dose; Refer to Table 2 – Infusion Treatment Guidelines for further management details.

c Patients with intolerable or persistent Grade 2 drug-related AE may hold study medication at physician discretion. Permanently discontinue study drug for persistent Grade 2 adverse reactions for which treatment with study drug has been held, that do not recover to Grade 0-1 within 12 weeks of the last dose.

Dosing interruptions are permitted in the case of medical / surgical events or logistical reasons not related to study therapy (e.g., elective surgery, unrelated medical events, patient vacation, and/or holidays). Subjects should be placed back on study therapy within 3 weeks of the scheduled interruption, unless otherwise discussed with the Sponsor. The reason for interruption should be documented in the patient's study record. Patients who permanently discontinue pembrolizumab may continue treatment with single agent sEphB4-HSA at the discretion of the treating physician.

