### 5.2.1.3 Dose Modification for sEphB4-HSA

sEphB4-HSA must be withheld for drug-related toxicities and severe or life-threatening AEs as per Table 3b below.

Dose modification scheme is as follows:

- (1) Dose level 0: 10 mg/Kg q week
- (2) Dose level -1: 5 mg/Kg q week
- (3) Dose level -2: 2.5 mg/Kg q week

Patients can have a maximum of 2 dose reductions for drug-related toxicity beyond which they will be removed from the study. If patient requires more than 2 dose reductions, they will be treated with single agent pembrolizumab or be removed from study treatment at the discretion of the treating physician.

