### **5.6 Subject Withdrawal/Discontinuation Criteria**

Subjects may withdraw consent at any time for any reason or be dropped from the trial at the discretion of the investigator should any untoward effect occur. In addition, a subject may be withdrawn by the investigator or the Sponsor if enrollment into the trial is inappropriate, the trial plan is violated, or for administrative and/or other safety reasons. Specific details regarding discontinuation or withdrawal are provided in Section 7.1.4 – Other Procedures.

A subject must be discontinued from the trial for any of the following reasons:

- The subject or legal representative (such as a parent or legal guardian) withdraws consent.
- Confirmed radiographic disease progression

*Note:* For unconfirmed radiographic disease progression, imaging should be repeated after 2 additional cycles of study treatments in order to confirm progressive disease.

*Note:* A subject may be granted an exception to continue on treatment with confirmed radiographic progression if clinically stable or clinically improved,

- Unacceptable adverse experiences as described in Section 5.2.1.2
- Intercurrent illness that prevents further administration of treatment
- Investigator's decision to withdraw the subject
- The subject has a confirmed positive serum pregnancy test
- Noncompliance with trial treatment or procedure requirements
- The subject is lost to follow-up
- Completed 24 months of uninterrupted treatment with pembrolizumab or 35 administrations of study medication, whichever is later.

*Note: 24 months of study medication is calculated from the date of first dose. Subjects who stop pembrolizumab after 24 months may be eligible for up to one year of additional study treatment if they progress after stopping study treatment provided they meet the requirements detailed in Section 7.1.5.5*

- Administrative reasons

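### After a pembrolizumab infusion reaction, or when a third sEphB4-HSA dose reduction is needed, the protocol contradicts itself on whether the other drug may continue

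*Combined protocol and SAP*

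**What the plan says.** **Pembrolizumab infusion reactions.** The table in Section 5.4.1 covers reactions to pembrolizumab. For Grades 3 and 4 it says "Subject is permanently discontinued from further trial treatment administration". For Grade 2 it says "Subjects who develop Grade 2 toxicity despite adequate premedication should be permanently discontinued from further trial treatment administration". Section 5.2.1.2 handles the same events in its dose-modification table: pembrolizumab stops permanently for Grade 3-4, or for Grade 2 that occurs despite premedication. The section then closes with "Patients who permanently discontinue pembrolizumab may continue treatment with single agent sEphB4-HSA at the discretion of the treating physician".

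**Repeated sEphB4-HSA dose reductions.** Section 5.2.1.3 says "Patients can have a maximum of 2 dose reductions for drug-related toxicity beyond which they will be removed from the study". The next sentence, about the same patients, says "they will be treated with single agent pembrolizumab or be removed from study treatment at the discretion of the treating physician".

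**Discontinuation from the trial.** Section 5.6 lists reasons for which a subject must be discontinued from the trial. The toxicity item reads "Unacceptable adverse experiences as described in Section 5.2.1.2". Section 5.2.1.3 is not cited there.

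**The concern.** A site dealing with a severe pembrolizumab infusion reaction can find one section that ends all trial treatment and another that leaves sEphB4-HSA available. Whether the patient receives further infusions of the other agent then depends on which section the site reads. A patient who would need a third sEphB4-HSA reduction faces a similar split: one sentence takes the patient off the study, and the next keeps the patient on pembrolizumab.

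The same terms feed the analysis. The safety endpoint in Section 4.2.3.1 is the rate of treatment-related toxicity that leads to stopping therapy. The monitoring rule in Section 8.2 counts toxicity that leads to treatment discontinuation before the third course. Section 8.2 also classes as non-responders those patients removed from the trial for unacceptable toxicity before they are evaluable. If sites apply different stopping rules to the same event, these counts partly reflect site interpretation.

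**Working it through.** The point rests on wording, so the check is to set the passages side by side.

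**Step 1: what trial treatment covers.** Section 5.2 says "The treatment to be used in this trial is outlined below in Table 2". That table is titled as the trial treatment and lists both pembrolizumab and sEphB4-HSA. On its plain wording, ending trial treatment ends both drugs.

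**Step 2: one event, two rules.**

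| Pembrolizumab infusion reaction | Section 5.2.1.2 | Section 5.4.1 table |
|---|---|---|
| Grade 3-4 | Pembrolizumab stops; sEphB4-HSA alone may continue | All trial treatment stops |
| Grade 2 despite premedication | Pembrolizumab stops; sEphB4-HSA alone may continue | All trial treatment should stop |

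The permission in Section 5.2.1.2 has no exception for infusion reactions. A site that continues sEphB4-HSA complies with Section 5.2.1.2 and breaches Section 5.4.1.

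**Step 3: consecutive sentences in Section 5.2.1.3.** The dose levels run 0, -1 and -2, so two reductions are the most available. Both sentences therefore concern the patient for whom a third would be needed. The first removes that patient from the study. The second offers pembrolizumab alone or removal from study treatment. If the physician chooses pembrolizumab alone, the first sentence is breached. The second option also differs from the first sentence: Section 5.6 keeps patients who stop treatment in disease and survival follow-up, which removal from the study, read literally, would end.

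**Step 4: the cross-reference in Section 5.6.** The mandatory item points to Section 5.2.1.2, which itself permits continuation on the other drug. It does not say whether it means one drug, both drugs or participation, and it does not point to the sEphB4-HSA rules.

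**Step 5: link to the monitoring rule.** The toxicity boundary in Section 8.2 can be reproduced. With alpha = beta = 0.10, p0 = 0.10 and pa = 0.30,

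N_X = X + [X ln(pa/p0) - ln((1 - beta)/alpha)] / [-ln((1 - pa)/(1 - p0))].

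This gives 7.37, 12.74, 18.11 and 23.49 for X = 3, 4, 5 and 6. Rounded down, these are the tabulated 7, 12, 18 and 23, so the boundary arithmetic is sound. What is unclear is the input. If a first-course infusion reaction ends all treatment, it counts as an event. If sEphB4-HSA continues alone into the third course, Section 8.2 does not say whether it counts. With three events needed among the first 7 patients, classifying one patient differently can decide whether the safety review starts.

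**The case against.** **The permission is only a permission.** Section 5.2.1.2 says the other drug may continue. A site that stops both drugs after a severe infusion reaction complies with both sections, so the table in Section 5.4.1 could be a specific exception. This stands in part: the clash is between a mandatory stop and an unqualified permission. But no exception is written. The alternative repair, reading trial treatment in that table as pembrolizumab alone, gives the opposite answer for sEphB4-HSA.

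**Section 5.4.1 is guidance.** It calls its measures suggested and refers to Section 5.2.1 for dose modification. However, that reference follows a note about unrelated events, and a footnote in Section 5.2.1.2 sends the reader back to the infusion reaction table. Neither section is given precedence.

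**Section 5.6 may not conflict at all.** This objection has force. Unacceptable adverse experiences are not defined in Section 5.2.1.2. Section 8.2 defines unacceptable toxicity as drug-related Grade 3 or more that does not resolve within 12 weeks, which an infusion reaction that resolves would not meet. Section 5.6 also uses discontinuation from the trial loosely: its list includes completing 24 months of treatment, and patients stay in follow-up. This limb is an unclear cross-reference, not a proven contradiction. The missing citation of Section 5.2.1.3 is likewise not a safety gap, since that section has its own rules, Section 5.2 makes unacceptable toxicity a general reason to stop, and Section 5.6 allows the investigator to withdraw any subject.

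**The endpoint terms are vague in any case.** Whether stopping one drug counts as discontinuation would need defining even if every management passage agreed. That is correct. The conflict adds to the problem and is not its only source.

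**Conclusion.** Two contradictions are established from the text: Section 5.4.1 against Section 5.2.1.2 for pembrolizumab infusion reactions of Grade 3-4, or Grade 2 despite premedication; and the two sentences of Section 5.2.1.3 for patients needing more than two sEphB4-HSA reductions. The first assumes that trial treatment means both drugs, as Section 5.2 lists them. The Section 5.6 item is unclear, and confidence in that limb is lower.

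A reader might infer that every patient who permanently stops one drug for toxicity meets conflicting rules, and might size this from the anticipated discontinuation rates of 10% (Section 8.2) and at most 25% (Section 4.2.3.1): 25 x 0.10 = 2.5 and 25 x 0.25 = 6.25 patients per cohort. The documents do not support this. A patient who stops pembrolizumab for pneumonitis or nephritis never meets the infusion reaction table, and the Grade 4 hypertension rule names sEphB4-HSA as the drug to stop. The two rates are overall discontinuation rates for toxicity and do not isolate infusion reactions or a third dose reduction. No rate is given for those triggers, so the number affected cannot be stated.

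The effect on the non-responder rule is also limited, because a resolved infusion reaction would not meet the Section 8.2 definition of unacceptable toxicity. As the lung cohort is closed, the forward effect falls on the head and neck cohort and on any patients still on treatment. The change should be made because the instructions concern exposure after severe reactions and the remedy is cheap.

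**What to change.** Reconcile the following by amendment:

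- **Sections 5.4.1 and 5.2.1.2.** State, for a pembrolizumab infusion reaction of Grade 3-4 and of Grade 2 despite premedication, whether the stop applies to pembrolizumab or to both drugs, and use the same statement in both places.
- **Section 5.2.1.3.** Replace the two sentences on patients needing more than two reductions with one rule that separates stopping sEphB4-HSA, stopping all study treatment and leaving the study.
- **Section 5.6.** Make the toxicity item say whether it means one drug, both drugs or trial participation, and cite both 5.2.1.2 and 5.2.1.3.
- **Sections 4.2.3.1 and 8.2.** Use the same terms in the toxicity-discontinuation endpoint, the toxicity monitoring rule and the non-responder rule, and say whether stopping one drug counts.

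The sponsor decides which clinical rule applies to each trigger; this review takes no position on that. The cost is a wording amendment, with no new data or procedures.
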